5.2.3. Analysis of the primary endpoint

The description of patients' perception of their treatment for NVAf will be achieved using the PACT-Q2 questionnaire.

For this, comparisons of paired samples (Student's paired t-test or the non-parametric Wilcoxon signed-rank test for data without a normal distribution) will be used to compare the scores obtained in the final assessment (continuation period) to those from the baseline assessment. Additional comparisons will be performed on the scores obtained in the intermediate assessment (initial period) in comparison to the baseline assessment, and the scores obtained in the final assessment in comparison to the intermediate assessment.

For the analysis of the primary endpoint, the instructions described below will be followed:

- Patients with a VKA end date before V1 date: patients who had the Pradaxa® initiation date (the date after VKA end date) within 7 days before V1 date, will be included in the corresponding analyses V1 vs V2 and/or V1 vs V3 and/or V2 vs V3, provided the new visit windows for V2 and/or V3 are met*.
- Patients with Pradaxa® initiation date (the date after VKA end date) = V1 date: all patients will be included in the corresponding analyses (V1 vs V2 and/or V1 vs V3 and/or V2 vs V3), provided the new visit windows for V2 and/or V3 are met*
- Patients with Pradaxa® initiation date (the date after VKA end date) after V1 date: all patients will be included in the corresponding analyses (V1 vs V2 and/or V1 vs V3 and/or V2 vs V3), provided the new visit windows for V2 and/or V3 are met*

* The acceptance windows days for visit 2 and visit 3 will be the following:

- V2 date - Day after VKA end date= 7-124 days
- V3 date - Day after VKA end date= 125-365 days

(NOTE: Due to Pradaxa® initiation date was not recorded in the eCRF, it is assumed that the initiation date of Pradaxa® is the day after the VKA end date)

These analyses will be performed based on the actual anticoagulant treatment received by the patients (i.e. “as-treated” analysis), so that patients who discontinue the initial anticoagulant treatment at the time of an assessment will be excluded from all analyses where data from that assessment is included.

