4.2. JUSTIFICATION FOR SAMPLE SIZE

The prospective collection is planned of data from approximately 1087 patients by approximately 200 principal investigators at cardiology and internal medicine centres and non-specialist centres that regularly prescribe dabigatran and VKAs for stroke prophylaxis in NVAF in accordance with the recommendations of the health authorities described in the therapeutic positioning report for direct oral anticoagulants (DOACs).

The participating centres are located in the autonomous communities of Catalonia, Galicia, Andalusia and the Basque Country.

As is established in the study protocol, due to the limited number of publications on the PACT-Q questionnaire (see reference studies in the Bibliography section of the protocol) and the absence of information on the clinical significance of variations in the PACT-Q scale, the sample size has been calculated using standardised mean differences. Specifically, in the context of this study, these represent the mean differences in the PACT-Q questionnaire score obtained at two different time points, divided by the corresponding standard deviations. Generally, a standardised effect size of 0.2 is considered to represent a small change, 0.5 represents a moderate change and 0.8 a large change.

Assuming a two-sided alpha level of 0.05 and a 20% loss to follow-up, a sample size of 1087 patients will give a statistical power of 90% for the detection of a standardised mean difference of 0.11 for the primary endpoint, the evaluation of PACT-Q2 questionnaire scores obtained during the final and baseline assessments.

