5.2.7. Statistical methodology

Categorical variables will be described by their absolute and relative frequencies. Continuous variables will be described using the mean and 95% confidence interval (95% CI), standard deviation, median, 25th and 75th percentiles, minimum and maximum, including the total number of valid values.

For the comparisons between visits for quantitative variables, parametric tests (Student's paired t-test) or non-parametric tests (Wilcoxon signed-rank test) shall be used, according to the characteristics of the variables in question.

A level

of statistical significance of 0.05 will be applied in all the statistical tests.

The data will be statistically analysed using the SAS statistical package, version 9.4 or later.

Due to the nature of this non-interventional study, there is no (confirmatory) hypothesis testing foreseen in a strict statistical sense. Analyses are descriptive in nature and confidence intervals and p-values from statistical models are used for exploratory purposes.

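### The primary test is chosen by an undefined normality check and can move away from the mean change on which the study was sized

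*SAP*

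**What the plan says.** SAP section 5.2.3 compares PACT-Q2 scores between visits with Student's paired t-test or "the non-parametric Wilcoxon signed-rank test for data without a normal distribution". Section 5.2.7 repeats the choice for all between-visit comparisons of quantitative variables: the parametric or the non-parametric test "shall be used, according to the characteristics of the variables in question". The p-value footnote of Table 25 (section 6.4.1) allows either test. None of these places names a normality test, a graphical criterion or a threshold. None says whether normality is judged on the visit scores or on the paired change, or whether one choice holds for all six comparisons (two domains, three visit pairs).

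Section 4.2 defines its effect measure as "the mean differences in the PACT-Q questionnaire score obtained at two different time points, divided by the corresponding standard deviations" and claims "a statistical power of 90% for the detection of a standardised mean difference of 0.11 for the primary endpoint", comparing the final with the baseline assessment.

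Table 25 describes each visit's score by mean, SD, 95% CI, median, quartiles and range, but has no row for the paired change. Section 5.2.7 adds that no confirmatory testing is intended and that p-values serve exploration.

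**The concern.** The plan lets the data choose the test without stating the criterion, and the two candidates do not answer the same question. The paired t-test addresses the mean change, which is what section 4.2 is built on. The Wilcoxon signed-rank test addresses whether the change is distributed symmetrically about zero, and this is a test of the mean only when the change is symmetric about its centre. If the change is skewed, Wilcoxon can reject when the mean has not moved, or miss a mean change of the planned size.

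Three things are at stake. The p-value in Table 25 may not refer to the means printed beside it. Different rows may carry p-values from different tests. Two analysts could both follow the SAP and report different results. Normality is also a poor trigger here: with several hundred pairs the paired t-test does not need it, while bounded scores that move in steps can fail a normality test because of the steps alone.

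**Working it through.** **1. Reproduce the plan's sample size (section 4.2).** Inputs: two-sided alpha 0.05, 20% loss, power 90%, standardised mean difference 0.11.

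- Pairs: (1.960 + 1.282)² / 0.11² = 868.4, so 869.
- Enrolled: 869 / 0.80 = 1086.3, so 1087, as stated.
- Exact paired-t power at 869 pairs: 0.8996.

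The stated figure is right, and it belongs to the paired t-test.

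**2. Wilcoxon when the change is normal.** Its asymptotic relative efficiency is 3/π.

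- Power at 870 pairs: Φ(0.11 × √(870 × 3/π) − 1.960) = Φ(1.21) = 0.887. Simulation agrees, at about 88-89%.
- Pairs for a full 90%: about 870.3 × π/3, so 912, and 912 / 0.80 = 1140 enrolled.

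The loss under normality is about one percentage point.

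**3. How often would a formal check reject normality?** Section 6.2.6.3 scores Convenience on 9 five-level items (36 steps of 100/36 = 2.78 points) and Satisfaction on 7 (28 steps of 100/28 = 3.57 points). A normal change was rounded to these steps, with about 869 pairs, and tested by Shapiro-Wilk at 0.05. The SAP gives no SD of change, so the SDs are assumptions.

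| Assumed SD of change | Convenience | Satisfaction |
|---|---|---|
| 15 points | 99-100% | 99-100% |
| 20 points | 43% | 97% |
| 25 points | 22% | 52% |

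In item-level simulations with 870 pairs, the check on the visit scores rejected in 100% of runs in every scenario. On the change it rejected in 100% with a mild or strong ceiling, but in 30-99% when the change was near symmetric. So the answer depends on the SD and on which quantity is checked, and the SAP settles neither.

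**4. What Wilcoxon does when the change is skewed.** Simulations with about 869 pairs; the skewness values are assumptions.

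| Skewness of change | Wilcoxon power at a mean change of +0.11 SD (positive skew) | Wilcoxon rejection at zero mean change (either sign) |
|---|---|---|
| 0 (normal) | about 88% | about 5% |
| 0.3 | about 72% | 9-11% |
| 0.5 | about 59% | 14-17% |
| 1.0 | about 22% | 54-62% |

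The paired t-test stayed at about 89-93% power and 3-7% rejection at zero mean change.

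Other assumed shapes give the same pattern:

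- Unrounded gamma changes (870 pairs): power 51% and 14.5% at skewness +0.5 and +1.0; rejection at zero mean about 22% and 66-69% at ±0.5 and ±1.0.
- Two-component normal mixtures: power 73%, 61% and 28% at +0.4, +0.6 and +1.0.

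The reason is visible in the quantity that Wilcoxon tracks, the pseudomedian of the change. For the gamma shapes with a mean change of 0.11 SD, it is only 0.069 SD at skewness +0.5 and 0.028 SD at +1.0.

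**5. Where Wilcoxon does as well or better.** Power at 0.11 was 92% and 95% for t-distributed changes with 10 and 5 degrees of freedom, and 99-100% with skewness of −0.5 and −1.0. In the item-level scenarios, ceilings included, it was 86-94%, with the t-test at 85-93% in the same runs. The change in those scenarios had skewness of only about 0 to +0.25.

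**The case against.** A reader might infer that the rule will send practically every comparison to Wilcoxon, and that the study therefore lacks its 90% power. The SAP does not support either step.

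It prescribes no formal normality test. A statistician judging from plots at about 869 pairs could keep the t-test under this wording. Even with Shapiro-Wilk, rejection can be as low as 22% for a rounded normal change. The step size is itself uncertain: section 6.2.6.3 scores Convenience on 9 items, while the Convenience tables list 13 (B1 to B11, C1 and C2). With 13 items (52 steps), rejection was about 35% at SD 15 and 13% at SD 20.

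Power falls materially only if the change is skewed in the direction of the effect, and nothing in the SAP shows the size or direction of any skew. For normal, heavy-tailed or ceiling-limited changes, Wilcoxon is close to the t-test or better.

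The remaining defences also carry weight. The SAP declares its p-values exploratory, the objective is descriptive, section 4.2 powers only final versus baseline, Table 25 shows medians as well as means, and a rank test is a respectable choice for scores built from ordinal items.

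All of this limits the size of the point. It does not supply the missing criterion, and it does not make a p-value that may concern a different quantity fit the effect on which the study was sized. An exploratory p-value should still refer to a known quantity.

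**Conclusion.** The point holds in a limited form. The choice of test for the primary endpoint is data-driven and undefined, and one of its two outcomes tests the mean difference of section 4.2 only if the change is symmetric. The planned 1087 patients and 90% power are correct for the paired t-test, so the sample size is not at fault.

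The consequence ranges from about one percentage point of power (normal change) to a p-value that answers a different question (clear skew: about 59% power at skewness +0.5 and 22% at +1.0, with 14-17% and 54-62% rejection at zero mean change for ±0.5 and ±1.0). Where the trial falls in that range rests on an SD and a skewness that the SAP does not give. A claim that Wilcoxon will nearly always be chosen, or that power will be lost, goes further than the document allows.

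Given the exploratory status, this is a cheap improvement of modest severity.

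**What to change.** - In sections 5.2.3 and 5.2.7 and the Table 25 footnote, specify the paired t-test on the mean change for all six comparisons, whatever the normality.
- Add a row to Table 25 for the mean paired change with its 95% CI in each comparison.
- Report the Wilcoxon signed-rank p-value as a labelled sensitivity analysis.

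The cost is SAP wording and a few table cells; no new data are needed, and the sizing in section 4.2 stands as written. The downside is that a few patients with large changes can pull the mean. The medians already in Table 25 and the Wilcoxon result would show this.

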3. STUDY OBJECTIVES

3.1. PRIMARY OBJECTIVE

The primary objective of this study is to describe patients' perception of their treatment for NVAf using the PACT-Q2 questionnaire at three time points: during the baseline period after the indication for Pradaxa[®], after approximately one month and during the continuation period:

- Visit 1 or baseline visit: when the patient is receiving treatment with VKAs for the prophylaxis of stroke/embolism and has changed treatment (baseline period to record the perception of treatment with VKAs). Patients will be enrolled in the study following the decision to start treatment with Pradaxa[®]. The decision to start treatment with Pradaxa[®] is based on the recommendations of the health authorities described in the therapeutic positioning report for NOACs.
- Visit 2 or initial period: when treatment with Pradaxa[®] has commenced (30-45 days).
- Visit 3 or continuation period: when continuing treatment with Pradaxa[®] (~180 days).

As indicated in section 1.8, Visit 2 data that were collected between 7 and 124 days after baseline will be included for analysis; Visit 3 data that were collected between 125 and 365 days after baseline will be included for analysis.

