5.2. DATA ANALYSIS AND STATISTICAL TESTS

5.2.1. Changes in the planned analysis

The SAP version 1.0 of 2nd February 2018 has been modified, according an express request of the sponsor.

The following sections have been modified:

- Section 1.8, Study Design: the valid visit windows between initiation date of Pradaxa® and Visit 2 / Visit 3 have been defined
- Section 1.12, Study schedule: the dates have been modified according the real dates
- Section 3.1, Primary Objective: the valid visit windows between initiation date of Pradaxa® and Visit 2 / Visit 3 have been defined
-
- Section 5.2.7, Statistical methodology: an explanatory note about the exploratory purposes of the analysis has been added.
- Section 6.1, Study population:
 - The valid VKA end date have been defined in inclusion criterion 4
 - The need of having the PACT-Q2 in all the study visits has been deleted
- Section 6.2.1 and 6.2.2, Socio-demographic data and Anthropometric data and vital signs: the p-value between males and females has been deleted in Table 2, Table 4 and Table 5.
- Section 6.2.1, Socio-demographic data: a categorisation about age (≤ 65 or > 65 years) has been added in Table 2.
- Section 6.2.6, Scales: the number of section 6.2.6.3 has been updated.
- Section 6.2.6.3, PACT-Q2 Questionnaire at Baseline: the title of the section and the title of Table 15, Table 16 and Table 17 have been changed, adding “at Baseline”.
- Section 6.3.1, Treatment with Pradaxa®: the header cells have been changed, deleting the specification of the period days in each visit.
- Section 6.3.2.1, PACT-Q2 Questionnaire at Follow-up: the title of the section has been changed, adding “at Follow-up”.
- Section 0, Analysis of the Secondary endpoints:
 - A categorisation about age (≤ 65 or > 65 years) has been added in Table 26.
 - The reference to the Thromboembolic risk (CHA2DS2-VASc) section has been updated in Table 26.
-

- Section 8.2, Reasons for Discontinuing Pradaxa®: the header cells have been changed, deleting the specification of the period days in each visit.

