5.2.2. Samples for analysis

The analyses will be performed on a single sample of assessable patients (eligible patients terminology is used in the Study Protocol), which will include all patients who meet the selection criteria.

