For the criteria that are not assessable from data reported in the eCRF, patients in whom the investigator indicates criterion non-compliance in the “Selection criteria” section of the eCRF will be excluded.

[figure not shown]
Table 1. Recruited and assessable patients	
n (%)	
Patients recruited	
Non-assessable patients	
Patients who have not granted informed consent in writing prior to enrolment	
Patients under 18 years of age or not diagnosed with NVAf	
Patients who have not been treated continuously with VKAs for stroke prophylaxis for at least six months prior to the baseline visit	
Patients who were not switching to Pradaxa	
Patients receiving Pradaxa® or VKAs for any reason other than stroke prophylaxis in NVAf	
Patients with contraindications for the use of Pradaxa® or VKAs described in the Summary of Product Characteristics (SmPC)	
Patients who are participating in any clinical trial of an investigational medicinal product or medical device	
Assessable patients	
Patients for the safety sample¹	

Note: A single patient may simultaneously be classified as non-assessable for more than one reason.

¹ *All patients participating in the study with follow-up data*

The figure below is a flow diagram of study patients, which will indicate the number of recruited and assessable patients, as well as the number of patients excluded from the study.

Figure 1. Flow diagram of patients

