D6. What is your degree of satisfaction with the presentation of your anticoagulant treatment (pill to be taken orally/injections)?					
D7. In general, what is your degree of satisfactions with your anticoagulant treatment?					

The table below will describe the scores obtained in the 2 domains of the PACT-Q2 questionnaire at both time points during follow-up:

Table 24. PACT-Q2 questionnaire score¹ during follow-up		
DOMAINS	Visit 2	Visit 3
Convenience		
Mean (SD)		
95% CI		
Median (P25; P75)		
(Min; Max)		
Valid N		
Satisfaction with the anticoagulant treatment		
Mean (SD)		
95% CI		
Median (P25; P75)		
(Min; Max)		
Valid N		

¹ Range from 0 to 100

6.4. ANALYSIS OF THE PRIMARY ENDPOINT: PERCEPTION OF TREATMENT FOR NVAF USING THE PACT-Q2 QUESTIONNAIRE

This section will analyse the primary objective of the study, which is to describe patients' perception of their treatment for NVAF using the PACT-Q2 questionnaire at three time points: during the baseline period after the indication for Pradaxa®, after approximately one month and during the continuation period.

For the analysis of the primary endpoint, the instructions described in section 5.2.3 will be followed.

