6.4.1. PACT-Q2 questionnaire scores during follow-up

Table 25. Evolution of PACT-Q2 questionnaire scores				
DOMAINS	Visit 1	Visit 2	Visit 3	p¹
COMPARISONS for VISIT 1 vs VISIT 2				
Convenience (range from 0 to 100)				
Mean (SD)		--		
95% CI		--		
Median (P25; P75)		--		
(Min; Max)		--		
Valid N		--		
Satisfaction with anticoagulant treatment (range from 0 to 100)				
Mean (SD)		--		
95% CI		--		
Median (P25; P75)		--		
(Min; Max)		--		
Valid N		--		
COMPARISONS for VISIT 1 vs VISIT 3				
Convenience (range from 0 to 100)				
Mean (SD)			--	
95% CI			--	
Median (P25; P75)			--	
(Min; Max)			--	
Valid N			--	
Satisfaction with anticoagulant treatment (range from 0 to 100)				
Mean (SD)			--	

Table 25. Evolution of PACT-Q2 questionnaire scores				
DOMAINS	Visit 1	Visit 2	Visit 3	p¹
95% CI			--	
Median (P25; P75)			--	
(Min; Max)			--	
Valid N			--	
COMPARISONS for VISIT 2 vs VISIT 3				
Convenience (range from 0 to 100)				
Mean (SD)	--			
95% CI	--			
Median (P25; P75)	--			
(Min; Max)	--			
Valid N	--			
Satisfaction with anticoagulant treatment (range from 0 to 100)				
Mean (SD)	--			
95% CI	--			
Median (P25; P75)	--			
(Min; Max)	--			
Valid N	--			

¹ Student's t-test or Wilcoxon test

NOTE: Patients without dates in range in each visit, will be excluded of the comparisons involved

Figure 6. Evolution of PACT-Q2 questionnaire scores
(Line graph for the 2 domains at the 3 study time points)

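### Does limiting the baseline-to-final PACT-Q2 comparison to patients still on Pradaxa, with no sample named for Figure 6, call for a change to the plan?

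*SAP*

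**What the plan says.** Section 5.2.2 names one population: "The analyses will be performed on a single sample of assessable patients". Section 5.2.3 then defines who enters each paired comparison:

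- Visit 2 and Visit 3 must fall 7–124 and 125–365 days after the assumed start of Pradaxa.
- If that start precedes Visit 1, it may do so by at most 7 days.
- The as-treated rule covers those "who discontinue the initial anticoagulant treatment at the time of an assessment will be excluded from all analyses where data from that assessment is included".

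Section 5.2.8 rules out imputation, so a patient without a score also drops out. Section 6.4 points back: "For the analysis of the primary endpoint, the instructions described in section 5.2.3 will be followed". The note under Table 25 repeats only the date rule: "Patients without dates in range in each visit, will be excluded of the comparisons involved". Figure 6 is specified as "Line graph for the 2 domains at the 3 study time points" and nothing more.

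Two other places bear on the point. Section 3.1 describes the final time point as "Visit 3 or continuation period: when continuing treatment with Pradaxa". The change list in section 5.2.1 records that "The need of having the PACT-Q2 in all the study visits has been deleted", so the three pairwise sets may contain different patients.

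**The concern.** The endpoint is how patients perceive their treatment, and the filter is whether they are still taking it. The two may well be linked. If patients who stop differ in perception from those who stay, the mean change from Visit 1 to Visit 3 describes those who stayed and not everyone who switched.

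Three features make this look like a gap:

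- A reader of Table 25 alone learns the date rule but not that patients off treatment are absent.
- Figure 6 draws one line per domain through three visits. Table 25 will hold two means per visit (each visit enters two comparisons), and Tables 17 and 24 may give a third. The figure does not say which is plotted.
- Sections 5.2.3 and 6.4 contain no count of exclusions by reason, no scores of excluded patients beside those retained, and no sensitivity analysis.

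At stake is the reading of a small observed change. Section 4.2 sizes the study for 0.11 SD, and a selection shift of that order could create or hide such a change.

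**Working it through.** **1. The plan's own figure.** Section 4.2 gives two-sided alpha 0.05, power 90%, a standardised paired difference of 0.11 and 20% loss.

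- Pairs: ((1.960 + 1.282) / 0.11)² = 868.4, rounded up to 869.
- Enrolled: 869 / 0.80 = 1086.25, rounded up to 1087, which matches.
- The 95% half-width for a mean change with 870 pairs is 1.963 / √870 = 0.067 SD.

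**2. Is there a contradiction?** Section 5.2.2 names the parent sample, section 5.2.3 says which of its members enter each comparison, section 5.2.8 limits the analysis to available data, and section 6.4 refers back to 5.2.3. Table 25 prints a Valid N in each block. A subset of one sample does not conflict with that sample.

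**3. How large could the shift be?** The SAP gives no stopping rate and no correlation, so every input here is assumed. Let stopping follow a logistic model in the standardised Visit 2 change. Then

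shift (retained minus all) = correlation × share stopping × gap in Visit 2 change between retained patients and stoppers.

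With correlation 0.6:

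| Log-odds slope per SD | 5% stop | 10% | 15% | 20% |
|---|---|---|---|---|
| 0.25 | 0.007 | 0.015 | 0.022 | 0.030 |
| 0.5 | 0.015 | 0.029 | 0.044 | 0.058 |
| 1.0 | 0.028 | 0.055 | 0.080 | 0.104 |

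The largest cell is 0.6 × 0.20 × 0.87 = 0.104. The sign reverses with the slope, and slope 0 gives 0. Two of the 12 cells exceed 0.067 and none reaches the 0.2 that section 4.2 calls a small change. Correlations of 0.4 to 0.8 widen the range to 0.005–0.139.

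A cruder route assumes directly how far the excluded patients' change differs: shift = share excluded × difference. At 20% excluded, differences of 0.2, 0.5 and 0.8 SD give 0.04, 0.10 and 0.16 SD. At 40% excluded they give 0.08, 0.20 and 0.32 SD. Size alone therefore does not dismiss the concern. What the result is meant to describe decides it.

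**4. What can be recovered from the planned tables?** Table 17 gives the Visit 1 mean and Valid N for the assessable sample. Table 25 gives them for the Visit 1 versus Visit 3 set. So

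excluded mean = (N₁₇ × mean₁₇ − N₂₅ × mean₂₅) / (N₁₇ − N₂₅).

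If means are printed to one decimal (an assumption), with 1087 and 870 patients, the worst rounding error is (1087 × 0.05 + 870 × 0.05) / 217 = 0.45 points on the 0–100 scale. Table 26 counts discontinuations, and Table 61 lists reasons by visit. Figure 1 shows assessable patients "as well as the number of patients excluded from the study". Two things cannot be recovered: the split of baseline scores by reason for exclusion, and the excluded patients' Visit 2 scores.

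**5. What would a mixed model add?** Fitted to on-Pradaxa scores, it assumes missing at random and estimates the score stoppers would have had if they had continued. That is not the experience of all switchers, which is the quantity said to be at risk. In simulation, when half of the stopping precedes Visit 2, the model removes only about half of the shift.

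**6. Figure 6.** If excluded patients' Visit 1 scores differ by an assumed 0.25 SD, the plotted Visit 1 mean moves by 0.05 × 0.25 = 0.0125 SD to 0.20 × 0.25 = 0.05 SD, depending on the set chosen.

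**The case for a change.** The best case for a change is that it costs little and fits a descriptive study, where readers must know whom the description covers. A table of included and excluded patients uses data already collected. With 217 excluded and 870 retained, its half-width would be 1.96 × √(1/217 + 1/870) = 0.15 SD, enough to show a gap of about 0.48 SD (slope 0.5). Subtracting Table 25 from Table 17 mixes patients who stopped with those who missed a visit or came outside the window.

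The facts in this stand. Figure 6 names no sample, the Table 25 note is incomplete when read alone, and the subtraction does not separate reasons.

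The step from there to a defect does not hold. The as-treated rule binds through section 5.2.3 whether or not a footnote repeats it. The absence of a comparison cannot be shown either, because sections 5.2.5 and 6.6 and Tables 27–54 are not visible. The table is also less decisive where stopping is rare: with 54 stoppers the half-width is 0.27 SD, against an expected gap of 0.25 SD at slope 0.25.

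**Conclusion.** No change is called for. The restriction to patients still on treatment is declared and agrees with the definition of Visit 3 in section 3.1. Section 5.2.7 describes the analyses as exploratory, so no error rate is affected. The result describes patients who continue Pradaxa, and for that purpose it is sound as planned.

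The shift relative to all switchers is unknown in size and direction: 0.007–0.104 SD in the modelled cases at correlation 0.6, more under cruder assumptions, and zero if stopping is unrelated to perception. All of these rest on assumed inputs. Neither the extra table nor the mixed model would alter the planned estimate, and the model would not estimate the all-switchers quantity.

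What remains is reporting detail. Whoever produces Figure 6 has to choose a set and would ordinarily label it with its N. A reader of Table 25 finds the as-treated rule through the cross-reference in section 6.4. This conclusion takes the initial anticoagulant treatment to mean Pradaxa at Visits 2 and 3, the only reading that fits section 3.1.
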